Therefore, we propose to provide structural group educations focus on accurate BP measurement, provided with validated home BP device, with regular reassessment of BP measurement technique. We are interested to find out whether the proposed intervention can lower BP and sustain high quality HBPM.

Study Aims and Objectives:

We aims at comparing providing validated home BP device, followed by group education of self-BP monitoring and regular assessment accuracy of BP monitoring, which may possibly improve BP control rate of patients with uncontrolled hypertension in primary care setting. We would also like to evaluate whether the quality of BP measurement is sustainable, any change in biochemical markers, clinic BP readings in 6 months, 12 months and 18 months interval. We would also find out patients' view on home BP monitoring and the education program.

Research Questions

1. Do the people with uncontrolled BP have higher control rate after provision of validated BP device followed by education and assessment of BP measurement technique?
2. Are there improvements in the clinic BP body weight, BMI, biochemical markers followed by the HBPM education program?
3. Can quality of HBPM be sustainable by education followed by regular reassessment?
4. What is patients' view on HBPM?

Methods

We adopt prospective longitudinal randomized control trial. Subjects from four general outpatient clinics (GOPCs) located in urban residential area will be involved in the study.

Study Practices and randomization procedure

We aimed to determine the effectiveness of HBPM education and provision of validated home BP device. Since the intervention involve doctors, nurses and patient cooperation, cluster (using one clinic as one cluster) approach is utilized to minimize risk of treatment contamination. Three clinics are randomly assigned as intervention clinic and the other three will be assigned as usual care clinic. (Appendix 1) To avoid contamination, separate protocols will be sent to individual clinics assigned to intervention and control. The Research helper will assist subject recruitment and data collection. The measurements and lab test will be performed by local clinic nurses and doctors in control clinics.

Research Subjects Recruitment

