Clinic nurses will assess the self-monitoring technique, home BP records, body weight and BMI and the clinic BP levels

4. 18 months post intervention

The above measurement will be collected via questionnaires by clinic nurses and research helper. Medical history includes diabetes mellitus, manifest cardiovascular disease (namely ischaemic heart disease, cerebral vascular disease, and peripheral vascular disease), current medication including antihypertensives drugs, lipid lowering agents, and antiplatelet drugs, laboratory test (6 to 18 months post intervention) results including fasting blood sugar, glycemic haemoglobin level, lipid profile will be collected by investigators via computerized patient record.

Data analysis

The Outcome Measurement includes

1. Blood pressure control rate (Primary outcome)
2. Change in clinic mean systolic and diastolic BP between baseline and each of the follow up point
3. Accuracy of HBPM by standard checklist in 1-3 months and 9-12 months post-intervention
4. Practice of HBPM 6-months post-intervention
5. Change in biochemical markers

6. Change in Body Weight and BMI
7. Adverse effect (reported by research subjects)

Sample size calculation will be based on the mean difference in blood pressure between intervention and controls at 9-12 months after baseline. Accounting for the clustering effect by practice, the intraclass correlation (ICC) for the intra-cluster correlation in primary care setting was taken as 0.01 which was a median estimate reported in previous study (24). In order to have 80% power and 5% false positive error to detect a difference in blood pressure of 3mmHg with assumed standard deviation of 5mmHg, there will be 216 subjects (25) which will be obtained by sampling 6 general outpatient clinics randomly, with 36 subjects each clinic in intervention group and 36 subjects each clinic in control group. Assuming 20% of attrition rate for 6-12 months follow-up, we need to recruit 45 subjects in each group per clinic at baseline, in total of 270 subjects.

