Descriptive statistics including mean, standard deviation of continuous outcomes and proportion of dichotomous outcomes will be calculated. Primary analysis will be an intention-to-treat analysis of the difference in outcomes between groups at 6-18 months after baseline. As with repeated measurement for patients, generalized estimating equation models using identify link will be conducted to assess differences in continuous outcomes within-group and between groups, adjusting for baseline patients' characteristics and clustering of patients per practice. Generalized estimating equation models using logistic link will be conducted to analyze differences within-group and between groups for dichotomous outcomes, adjusting for same sets of patients' characteristics. Missing values will be imputed using last value carrying forward method. Repeated analysis will be done for per-protocol analysis.

All statistical analyses will be performed using SPSS Windows 21.0 program. P-value less than 0.05 will be considered statistically significant.

Data collection throughout the trial

Demographic Questions	Measurements
Duration of HT	BMI (BH/ BW)
Past Medical history	Waist circumference
Contra-indications to antihypertensive drugs	Clinic BP (sitting position/ standing position)
Current HT medication	Lab Test: FBS, Lipid profile, eGFR, Urine PCR
	HBPM Technique

Qualitative Study on Evaluation of the Programme

Individual interviews (30-45 minutes) to 30 subjects from intervention group will be performed 2-4 months after education seminar and 1st doctor consultation (whenever later). Views on the self-monitoring, home BP reading interpretation blood pressure treatment targets, will be collected.

Sampling Method: 30 subjects with uncontrolled hypertension, some have attended intervention group, with different sex, age group, health literacy and occupations will be interviewed.

Semi-structured interview guide for patients and their family caregivers using social cognitive theory(26) as framework

Framework	Interview questions
Overall experience & attitude	Does high blood pressure (BP) border you? Why? Tell us about your general impression on Self-blood pressure monitoring (SBPM)

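### The logistic model that tests the primary outcome does not name clinic clustering although clinics are randomised; read literally its error exceeds 5%, and with six clinics the remedy needs a small-sample method

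*Protocol*

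**What the plan says.** - **Unit of allocation.** Protocol, Study Practices and randomization procedure: a "cluster (using one clinic as one cluster) approach is utilized to minimize risk of treatment contamination". The same paragraph adds: "Three clinics are randomly assigned as intervention clinic and the other three will be assigned as usual care clinic".
- **Primary outcome.** Protocol, Data analysis, item 1 of the outcome list: "Blood pressure control rate (Primary outcome". Control is a yes/no state for each patient, so this outcome falls under the rule for dichotomous outcomes.
- **Sizing.** Protocol, Data analysis: "the intraclass correlation (ICC) for the intra-cluster correlation in primary care setting was taken as 0.01", and the calculation is made "In order to have 80% power and 5% false positive error" on a difference in blood pressure of 3 mmHg with SD 5 mmHg. It arrives at 216 evaluable patients, 36 in each of six clinics, and 270 recruited.
- **Model for continuous outcomes.** Same section, GEE paragraph: identity link, adjusted for baseline patient characteristics and for "clustering of patients per practice".
- **Model for dichotomous outcomes.** The next sentence: GEE "using logistic link will be conducted to analyze differences within-group and between groups for dichotomous outcomes, adjusting for same sets of" patient characteristics. Clustering by clinic is not named.

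No other sentence in the protocol extends the clustering adjustment to the logistic model.

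**The concern.** The two adjacent model sentences differ on the feature that matters most in a clinic-randomised trial. The first lists two things to account for, patient characteristics and practice clustering. The second carries forward only the patient characteristics. The clinic is therefore named in the model for secondary outcomes such as mean blood pressure and not in the model for the primary one.

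The only correlation that the paragraph gives as its reason for using GEE is repeated measurement of the same patient. An analyst who follows the text would plausibly take the patient as the GEE subject. Patients of one clinic would then count as independent, the standard error of the treatment comparison would be too small, and the 0.05 threshold would not hold for the trial's main conclusion. Mean pressure and control rate could also disagree simply because one was analysed with clustering and the other without.

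**Working it through.** **Inputs from the protocol.** k = 3 clinics per arm; m = 36 evaluable and 45 recruited per clinic; ICC 0.01; difference 3 mmHg; SD 5 mmHg; 80% power; 5% error. Sidedness is not stated, so I take two-sided. Both values of m matter: 36 is the evaluable number, while intention-to-treat with last value carried forward could bring all 45 into the analysis.

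**Step 1: reproduce the stated sample size.** Design effect DE = 1 + (m − 1) × ICC = 1 + 35 × 0.01 = 1.35. A normal approximation needs 44 per arm before clustering; 44 × 1.35 = 59.4 per arm, or about 119-120 in total, which is not 216. A clinic-level comparison does give 216:
- SE = SD × √(2 × DE/(k × m)) = 5 × √(2 × 1.35/108) = 0.79 mmHg.
- Noncentrality = 3/0.79 = 3.79, on 2 × (3 − 1) = 4 df.
- Power is 79.9% at m = 35 and 80.7% at m = 36. So 36 is the smallest m that reaches 80%, and 6 × 36 = 216.
- Attrition: 216/0.80 = 270 and 36/0.80 = 45, both exact.

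The stated sizing is thus what one gets by treating the clinic as the unit, with 4 df.

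**Step 2: error if the primary test ignores clinic.** The standard error is too small by a factor √DE, and the actual two-sided error is 2 × (1 − Φ(1.96/√DE)). At ICC 0.01:
- m = 36: DE 1.35, √DE 1.16, error 2 × (1 − Φ(1.69)) = 9.2%.
- m = 45: DE 1.44, √DE 1.20, error 2 × (1 − Φ(1.63)) = 10.2%.

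The standard error is understated by 1 − 1/1.16 = 14% to 1 − 1/1.20 = 17%.

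The protocol gives no ICC for control rate, so the other rows are assumptions:

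| ICC | DE (m = 36 / 45) | Error (m = 36 / 45) |
|---|---|---|
| 0.005 | 1.175 / 1.22 | 7.1% / 7.6% |
| 0.01 | 1.35 / 1.44 | 9.2% / 10.2% |
| 0.02 | 1.70 / 1.88 | 13.3% / 15.3% |
| 0.05 | 2.75 / 3.20 | 23.7% / 27.3% |

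**Step 3: check with a binary outcome.** Simulation used beta-binomial clinics, 50% control, three clinics per arm, a log-odds Wald test ignoring clinic, and 40,000 runs. Rejection under the null at m = 36 / 45 was 8.7% / 9.4% at ICC 0.01, 13.3% / 14.9% at 0.02 and 23.7% / 27.0% at 0.05. With three repeated measures clustered on patient only (assumed within-patient correlation 0.5, ICC 0.01, m = 36) it was 11.4%.

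**Step 4: what the remedy must contain.** In the same single-time-point simulation, a clinic-clustered sandwich Wald test without small-sample correction rejected:
- ICC 0.01: 17.9% (m = 36) and 18.0% (m = 45)
- ICC 0.02: 18.2% and 18.1%
- ICC 0.05: 17.9% and 18.2%

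Fitted GEE models with clinic as cluster (ICC 0.01, m = 36, 1,500 runs) gave 19.3% and 19.9% at control rates of 30% and 50%. In those runs a clinic-level t test on 4 df gave 5.1% and 5.3%. A sandwich variance inflated by k/(k − 1), with a t reference on 4 df, gave about 4.7%.

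**The case against.** The strongest reply is that the second sentence is an ellipsis. It is written by reference back to the first and may be meant to change only the link function. The design and the sizing both treat the clinic as the cluster, so the authors probably did not intend to drop it. Read with full strictness, the logistic sentence does not name repeated measures either, so it states no cluster unit at all. A reader might infer that the protocol has decided to exclude the clinic from the primary analysis. The document does not support that: it names the clinic in one sentence and is silent in the next.

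That limits what can be said about intent, but it does not remove the point. The protocol fixes both models and words them differently. The phrase carried forward is confined to patient characteristics, which the preceding sentence lists separately from clustering. A statistical analysis plan may settle the matter, but the protocol text as it stands, followed as written, gives an invalid primary test.

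Two further objections stand in full. First, the ICC of 0.01 was stated for sizing on mean blood pressure. Applying it to control rate is borrowing, so 9-10% is conditional and not a property of the trial. Second, a reader might infer that the continuous model is a sound template and that copying its clustering phrase would cure the primary model. It would not: with six clinics an uncorrected sandwich test has about 18% error, worse than ignoring clinic at ICC 0.01 or 0.02. The continuous model has the same weakness unless a correction is specified for it.

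**Conclusion.** The point holds as a defect in the wording of the primary analysis. The sentence governing the primary outcome does not account for the unit of randomisation, while its neighbour does. Followed literally, the two-sided error is about 9-10% if an ICC of 0.01 applies to control rate, and about 7% to 27% over assumed ICCs of 0.005 to 0.05; it exceeds 5% for any positive ICC.

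This rests on three assumptions: two-sided testing; independence between patients of one clinic in the logistic model; and one arm per clinic with six clinics. On the last, the Methods mention four clinics, and the sample-size text could be read as placing both arms in each clinic. The three-against-three allocation and 6 × 45 = 270 support the reading used here.

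The correction belongs before analysis, because it decides whether the primary P value is valid. It must settle both the clinic level and the small number of clinics.

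**What to change.** Amend the logistic sentence so that the primary control-rate analysis accounts for clustering by clinic with a method valid for six clinics, and name the method. Either of these would serve:
- a clinic-level t test on 4 df, with patient characteristics handled by first adjusting at patient level and then comparing clinic summaries; or
- GEE with clinic as the cluster, a bias-corrected sandwich variance and a t reference on 4 df.

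Apply the same small-sample method to the continuous model, so that both sentences describe one approach. If the GEE route is chosen, confirm that the SPSS version named in the protocol can produce the correction.

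Recruitment and data collection do not change. The cost is a wider primary confidence interval. At ICC 0.01 its width relative to one that ignores clinic is roughly (2.776 × 1.16)/1.96 = 1.6 at 36 per clinic and (2.776 × 1.20)/1.96 = 1.7 at 45. For mean blood pressure, the sample size as reproduced above already allows for this.

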The recruitment of subjects and study workflow is shown in **Figure 1**. We include adult subjects aged above 18 years old on hypertensive treatment more than 12 months with uncontrolled hypertension and no previous HBPM on the day of recruitment. Uncontrolled hypertension is defined as BP > 140/90mmHg(19,20) in subjects age < 80; and BP > 150/90mmHg(21) in subjects age ≥ 80 . They will be invited to participate if they are willing and capable to perform home BP monitoring by themselves on daily basis. Appropriate subjects will be identified during doctor consultation and nurse consultations and subjects will be invited after normal consultation.

We exclude subjects who are unable to perform the home monitoring either by themselves; or have arrhythmias, unstable angina, serum creatinine > 250 mmol/l, orthostatic hypotension, severe left ventricular impairment, severe aortic stenosis and pregnancy.

Data Collection

Subjects enrollment and baseline assessment take place before randomization. Follow up data collection will be conducted 6 months, 12 months and 18 months after intervention.

Baseline Assessment

At baseline, patient age, sex, smoking habits, body mass index, waist circumference, education level, occupation, payment method, household income and number of household family members, health literacy by Chinese Health Literacy Scale for Chronic Care (22) will be collected via questionnaires by clinic nurses and research helper. Medical history includes diabetes mellitus, nephropathy, manifest cardiovascular disease (namely ischaemic heart disease, cerebral vascular disease, and peripheral vascular disease), current medication including antihypertensives drugs, lipid lowering agents, and antiplatelet drugs, laboratory test results including fasting blood sugar, glycemic haemoglobin level, lipid profile, serum creatinine level, presence of significant proteinuria will be collected by investigators via computerized patient record.

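### Last value carried forward in the primary analysis turns early dropouts into treatment failures, because every subject enters with uncontrolled blood pressure

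*Protocol*

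**What the plan says.** The Data analysis section sets the primary analysis: "Primary analysis will be an intention-to-treat analysis of the difference in outcomes between groups at 6-18 months after baseline". It uses generalized estimating equations, with a logistic link for dichotomous outcomes. It then states: "Missing values will be imputed using last value carrying forward method". The only further analysis it names is per-protocol ("Repeated analysis will be done for per-protocol analysis"), which does not deal with missing data. The first item in the list of outcomes, the blood pressure control rate, is marked as primary.

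Under Research Subjects Recruitment, subjects must be "on hypertensive treatment more than 12 months with uncontrolled hypertension", judged on the recruitment day. The limit is 140/90 mmHg below age 80 and 150/90 mmHg from age 80.

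The sample-size paragraph plans for loss: "Assuming 20% of attrition rate for 6-12 months follow-up". Follow-up is at 6, 12 and 18 months. The Intervention Group section also lists a clinic BP at a visit 1–3 months after training; no such visit is listed under Usual Care.

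**The concern.** Carrying the last value forward assumes that a subject's BP stays where it was last seen. That is especially hard to defend here, because the entry value was selected for being high. Even without the intervention, some subjects would be controlled later, through regression to the mean and the medication changes and counselling described under Usual Care. If a subject has no follow-up BP, the rule rejects that possibility and scores a failure.

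The estimated difference then depends on how many subjects each arm loses and when, as well as on the treatment effect. Unequal loss is plausible. Only the intervention arm has training sessions, daily home monitoring, a device to return and technique assessments. Allocation is by clinic, so retention may also differ by site.

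The rule also fills in outcomes nobody observed and lets the model count them as data, which overstates precision. All of this falls on the primary analysis of the primary outcome, and no missing-data sensitivity analysis is named that would reveal it.

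**Working it through.** **The plan's own figures.** With 3 clinics per arm, 36 subjects per clinic and ICC 0.01, the design effect is 1 + 35 × 0.01 = 1.35. The noncentrality is 3 / (5 × √(2 × 1.35/108)) = 3.795. On a noncentral t with 4 degrees of freedom (two-sided 5%, assumed), power is 80.7%, so the 216 evaluable subjects reproduce. Attrition: 216/0.8 = 270, so the plan expects to lose 54 of 270 subjects, or 27 of 135 per arm if loss is equal.

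**Assumptions.** The protocol gives no control rates and no split of dropout by arm or time, so those below are assumed. Dropout is taken as unrelated to outcome. Standard errors and error rates ignore clustering.

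**Step 1: all loss before any follow-up BP.** The carried value is the uncontrolled entry value, so an arm with true control rate *p* and loss *d* shows *p*(1 − *d*). The difference is *p*₁(1 − *d*₁) − *p*₀(1 − *d*₀), with 1 = intervention and 0 = control.

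| Loss, interv./control | True 60% v 45% (15 points) | True 50% v 50% (0 points) |
|---|---|---|
| 20% / 20% | 0.48 − 0.36 = 12.0 | 0.40 − 0.40 = 0 |
| 25% / 15% | 0.45 − 0.3825 = 6.75 | 0.375 − 0.425 = −5 |
| 30% / 10% | 0.42 − 0.405 = 1.5 | 0.35 − 0.45 = −10 |
| 10% / 30% | 0.54 − 0.315 = 22.5 | 0.45 − 0.35 = +10 |

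The sign can reverse when the true effect is smaller: 55% v 50% with 30%/10% loss gives 0.385 − 0.45 = −6.5 points.

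**Step 2: milder case.** Half of the dropouts leave before 6 months and carry the entry value; half leave before 12 months and carry their 6-month status. Assume underlying systolic BP is normal (mean 138, SD 10), visit error SD is 9, and entry requires a reading above 140. Follow-up SD is then about 12. The expected control rate is 35.1% without effect and 44.8% with a 3 mmHg effect, a true difference of 9.7 points. Each arm now shows *p*(1 − *d*/2).

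| Loss, interv./control | True 9.7 points | No effect |
|---|---|---|
| 20% / 20% | 8.7 | 0 |
| 25% / 15% | 6.7 | −1.8 |
| 30% / 10% | 4.7 | −3.5 |
| 10% / 30% | 12.7 | +3.5 |

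**Step 3: false-positive rate.** Take 40% control in both arms, loss of 30% (intervention) and 10% (control), all before follow-up, and 135 subjects per arm. The false difference is 0.28 − 0.36 = −8 points, with standard error √((0.28 × 0.72 + 0.36 × 0.64)/135) = 0.057. A nominal 5% test rejects about 29% of the time.

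**Step 4: precision.** At 60% v 45% with 20% loss in both arms, carry-forward gives √((0.48 × 0.52 + 0.36 × 0.64)/135) = 0.060. The 108 subjects per arm actually observed support √((0.60 × 0.40 + 0.45 × 0.55)/108) = 0.067.

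**Step 5: the 1–3 month reading.** Suppose it may be carried forward, and only the intervention arm has it. With 40% control in both arms and 20% loss in both, the control arm shows 0.40 × 0.80 = 32%. If 20% to 40% of intervention dropouts were controlled at 1–3 months, that arm shows 0.32 + 0.20 × 0.20 = 36% to 0.32 + 0.20 × 0.40 = 40%. That is a false gain of 4 to 8 points, with a type I error of about 11% to 28%.

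**The case against.** The largest figures are stress cases. They need every dropout to leave before follow-up and a 20-point imbalance in loss. The protocol gives a single 20% and nothing that supports such a split. At 25%/15% in the milder case, the false difference under no effect is about −1.8 points. With equal loss, no true effect and the same visits in both arms, carry-forward is unbiased and the type I error stays at 5%; with a real effect and equal loss it only attenuates. This stands: the bias is conditional and its direction is not fixed.

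The claim about standard errors also needs care. The model's standard error does match the sampling variation of the carry-forward estimate itself (0.058 against 0.059 in simulation at 40% v 55% with 20% loss). The shortfall is relative to what the observed data can say about the true difference. This stands as a clarification.

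Not every dropout is scored as a failure. Later dropouts carry their last follow-up status, and a few study baselines, taken as the mean of the second and third readings, may fall below the threshold. The milder model also uses only the systolic limit of 140, and its follow-up SD of about 12 differs from the SD of 5 in the sample-size paragraph. These points affect size only.

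The 1–3 month visit means that an intervention subject lost after it need not count as a failure. But it replaces one bias with another: the arms would carry different kinds of value, and equal dropout would no longer protect the comparison.

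Finally, the statistical analysis plan is not shown. That does not excuse the rule, because the protocol states it outright.

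**Conclusion.** The point holds. The protocol fixes a missing-data rule that, combined with its own entry criterion and primary outcome, makes the estimated control-rate difference depend on dropout. At the planned 20% loss, equal in both arms and all before follow-up, a true difference shrinks by one fifth; if half of the loss is that early, it shrinks by about one tenth. Unequal loss can hide most of a real effect, inflate it, reverse a small one, or create one where none exists. The standard error is understated by about 11% in the worked case (0.060 against 0.067). The sizes rest on assumed control rates and dropout patterns, on dropout unrelated to outcome, and, for standard errors and error rates, on ignoring clustering. The mechanism needs only the protocol's own rules and some subjects without a follow-up BP. This should be changed, and changing it is cheap.

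**What to change.** In the Data analysis section, remove last value carried forward from the primary analysis and replace it with methods valid under missing at random:

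- **Control rate:** multiply impute clinic BP by arm, with clinic, baseline BP and earlier visits in the imputation model. Derive control status from the imputed BP, fit the planned logistic GEE and combine the results.
- **Continuous BP:** fit a likelihood-based repeated-measures mixed model to all observed visits, without imputation. Multiple imputation followed by the planned GEE would also remove the fault.
- **Sensitivity:** keep carry-forward only here, state whether the entry value and the 1–3 month reading may be carried, and add at least one analysis that departs from missing at random.
- **Reporting:** give dropout by arm, clinic and visit.

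The cost is revised wording and some programming. With only three clinics per arm, the clinic term in the imputation model needs care. Intervals will be somewhat wider, as the observed data warrant. No new data are needed.

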Enhance Home Blood Pressure Monitoring Accuracy in uncontrolled Hypertension: a Randomized Controlled Trial

Background:

Being a highly prevalence global health problem, high blood pressure (BP) attributed to 13.5% of the global total premature death (1). Clinical findings in Hong Kong were shown to be comparable to the global situation. Locally, hypertension is the commonest chronic disease in Hong Kong with a prevalence of 27% among people aged 15 years or above. (2) It is the second commonest reason for consultation in Hong Kong primary care setting. (3) Control of BP to an optimal level is recommended to prevent irreversible cardiovascular event.

International guidelines including the European Society of Hypertension (EHS) (4), National Institute for Health and Clinical Excellence (NICE) (5) and the World Hypertension League (6) recommended appropriate use of home blood pressure monitoring (HBPM) in evaluate hypertension in certain clinical conditions. Systemic reviews have shown HBPM improve patients' BP control rate and compliance with treatment. (7,8) HBPM enables a more precise initial diagnosis of hypertension and more accurate titration of antihypertensive drug treatment (4), as shown by randomized control trials (9-12). Current Evidence suggested that blood pressure (BP) assessment are frequently inaccurate, with a high potential to misdiagnose a large segment of the population. (13). Therefore, the use of automated devices using oscillometry is recommended for HBPM (4).

As response to the recent promulgation by primary care clinicians (14), many patients with hypertension adopt HBPM (15). Local study also showed short term improvement of BP by one-off structured education program of home BP monitoring (16). However, sustainability of high quality HBPM technique remains unknown.

High quality HBPM depends on selection of validated device according to international recommendation; appropriate cuff size; conditions of measurement, correct procedure of measurement; and correct interpretation of HBPM readings. (4) Even with training, the use of standardized manual techniques (17) declines rapidly without regular retraining and accuracy testing (6). The accuracy of monitors and operators was prone to error, mostly due to mistakes by operator. (18)

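### Last value carried forward pulls the estimated loss of HBPM technique towards zero, and a difference test at P<0.05 cannot by itself show that technique was sustained

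*Protocol*

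**What the plan says.** Sustained technique is a stated aim in the Protocol, under Study Aims and Objectives: "evaluate whether the quality of BP measurement is sustainable". It is also research question 3: "Can quality of HBPM be sustainable by education followed by regular reassessment". The matching outcome, third in the list under Data analysis, is "Accuracy of HBPM by standard checklist in 1-3 months and 9-12 months post-intervention". Under Intervention Group, technique is assessed at the visit 1 to 3 months after training and again at 6, 12 and 18 months.

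The Data analysis section plans generalized estimating equations to "assess differences in continuous outcomes within-group and between groups" and, with a logistic link, to "analyze differences within-group and between groups for dichotomous outcomes". For all outcomes alike, "Missing values will be imputed using last value carrying forward method" and "P-value less than 0.05 will be considered statistically significant". The Protocol gives no tolerated loss of technique and no sample size for this question; its sample size rests on blood pressure. The Background states that technique "declines rapidly without regular retraining and accuracy testing".

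**The concern.** Two separate problems meet in this outcome.

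- **Imputation.** The quantity of interest is change in technique after the early assessment. Carrying the last score forward assumes no further change once a subject stops attending. People who stop attending also stop being reassessed, and the Background says that this is when technique deteriorates. The imputation therefore assumes the favourable answer to research question 3 for the subjects in whom it is least plausible.
- **Inference.** A test for difference can show a decline. Failing to find one is not evidence that quality was kept, and it becomes more likely as precision falls. Nothing in the sample size protects this question against low precision.

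At stake is a conclusion that education with regular reassessment keeps home measurement accurate, when the data could be compatible with a material loss.

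**Working it through.** **1. The plan's own sample size.** Inputs from Data analysis: difference 3 mmHg, SD 5 mmHg, ICC 0.01, 36 per clinic, six clinics, 80% power, 5% error (taken as two-sided), 20% attrition.

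- Design effect: 1 + (36 − 1) × 0.01 = 1.35.
- Standard error with three clinics (108 subjects) per arm: 5 × √(2 × 1.35/108) = 0.791. Non-centrality: 3/0.791 = 3.79.
- A t-test on 2 × (3 − 1) = 4 df has power 80.65%. With 35 per clinic it is 79.9%, so 36 is the smallest number that works and 216 is reproduced.
- 216/0.8 = 270, that is 135 recruited and 108 completing per arm. None of this concerns technique.

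**2. What carry-forward does to the estimate and interval.** Assumptions, because the Protocol gives no technique figures: correct technique falls from 80% to 70%; within-subject correlation ρ is 0.3 to 0.5; there are two assessments; 27 of 135 subjects (20%) have none after the first and decline like completers.

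- Estimate: 0.8 × 10 + 0.2 × 0 = 8 points instead of 10.
- Completers, ρ = 0.3: variance of change = 0.16 + 0.21 − 2 × 0.3 × √(0.16 × 0.21) = 0.26. Half-width = 1.96 × √(0.26/108) = 9.6 points.
- Carried forward, ρ = 0.3: the share of subjects who change among completers is 0.26 + 0.10² = 0.27. Variance = 0.8 × 0.27 − 0.08² = 0.2096. Half-width = 1.96 × √(0.2096/135) = 7.7 points.
- Test statistic: 0.10/0.0491 = 2.04 for completers and 0.08/0.0394 = 2.03 carried forward. The P-value hardly moves; the damage is a shrunken estimate and false precision.

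**3. If non-attenders decline more (assumed).** Completers lose 5 points and dropouts 30. The true loss is 0.8 × 5 + 0.2 × 30 = 10. Carry-forward shows 0.8 × 5 = 4; completers alone show 5. With 5% of subjects improving, P≥0.05 in about 73% of simulated trials.

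**4. What a non-significant change would mean.** With 108 completers and the fall from 80% to 70%:

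| ρ | Variance of change | SE | 95% half-width | Trials with P≥0.05 (simulated Wald test) |
|---|---|---|---|---|
| 0.3 | 0.260 | 0.0491 | 9.6 points | 47% |
| 0.5 | 0.187 | 0.0416 | 8.1 points | 31% |

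A normal approximation gives 47% and 33%. Other assumptions (5 to 10% of subjects improving, score McNemar test) give 33-52% for a 10-point fall and 74-82% for a 5-point fall.

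**5. What a margin rule would do.** Assume a 10-point margin for illustration.

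- A true 10-point loss would be called sustained about 2.5% of the time.
- With no true loss (80% at both times), variance = 2 × 0.16 × (1 − ρ) = 0.224 or 0.160, and SE = 0.0455 or 0.0385 for ρ = 0.3 or 0.5. The chance of meeting the margin is Φ(0.10/SE − 1.96) = 59% or 74%.

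**The case against.** **The Protocol never equates non-significance with 'sustained'.** A reader might infer that rule from the absence of any other, but the threshold is a general one for all outcomes. The analysis also includes between-group comparisons and descriptive statistics. A definition or margin for a non-primary outcome could properly sit in a SAP that is not shown, so its absence is not the fault. This stands. What remains is that carry-forward and the difference tests are written into the Protocol, and that technique visits are described only under Intervention Group, so the question is in effect one of change within that arm.

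**Carry-forward does not set every non-attender's change to zero.** That stronger reading fails, because technique is also assessed at 6, 12 and 18 months. A subject who leaves after 6 months carries a score that already contains any earlier decline. The 10-to-8 illustration is for subjects with nothing after the first assessment, and later dropout gives less shrinkage.

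**Shrinkage is not peculiar to this outcome.** This is correct: carry-forward freezes blood pressure, weight and laboratory values as well. What differs here is that zero change is the favourable answer.

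**The figures are assumed.** This is also correct. The design effect of 1.35 belongs to the between-arm blood pressure calculation. Stable clinic effects cancel in within-subject change, so it is not applied to the technique figures. The two-visit paired test also simplifies the planned repeated-measures model.

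**Analysing observed data alone does not cure informative dropout.** In step 3 it shows 5 against a true 10, hardly better than 4. This stands, and it is why the fix includes a sensitivity analysis.

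**Conclusion.** The point holds in limited form. Followed as written, the plan biases the estimated loss of technique towards zero and overstates its precision, against the Protocol's own premise about decline. With 20% lacking any later assessment and declining like completers, the estimate shrinks by a fifth (10 points to 8) and the half-width falls from 9.6 to 7.7 points at ρ = 0.3. Both effects are smaller if subjects leave later; the bias is larger if non-attenders decline more.

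Separately, a non-significant change would be weak evidence of sustained quality: a true 10-point loss would give P≥0.05 in about 31-47% of trials under the stated assumptions.

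Two further inferences are not supported. The documents do not show that the investigators intend to report non-significance as success. Nor does carry-forward itself raise the chance of a non-significant result when dropouts resemble completers. The title speaks of enhancing accuracy; sustainability comes from the aims and research question 3. This is a secondary question, and the change is worth making without being critical to the trial.

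**What to change.** For the technique outcome:

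1. Drop carry-forward and fit the planned GEE to all observed assessments.
2. Add a sensitivity analysis that assumes greater decline among subjects without later assessments.
3. Report the change from the 1-3 month assessment to the latest one with its 95% confidence interval. Say which visit counts as the latest, since the outcome list gives 9-12 months while the visits are at 6, 12 and 18 months.
4. State that 'sustained' will not be claimed from a non-significant P-value. It will be claimed only if the interval excludes a loss larger than a margin fixed before the data are seen. Otherwise report the estimate and interval without the claim.

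No new data are needed. The cost is a little more analysis, wider (but honest) intervals and the need to justify a margin. At about 108 completers even a 10-point margin would be met in only 59-74% of trials with no true loss, under the assumptions above, so a tighter one is unlikely to be shown.
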